11.1.1 Primary variable

Change from baseline in the mean NRS score at Week 4 of the double-blind period

11.1.1.1 Primary analysis

Using the data obtained up to Week 4 of the double-blind period, the superiority of the MR13A9 0.5 µg/kg group to the placebo group will be confirmed by performing the analysis using a mixed-effects model for repeated measures (MMRM) with change from baseline in the mean NRS score at each time point as an objective variable; treatment group, time point, and treatment group-by-time point interaction as fixed effects; baseline mean NRS score and the

presence or absence of prior treatment with nalfurafine hydrochloride as a dynamic allocation factor as a covariate; and subject as a random effect.

The analysis will include all available data obtained at each time point from Week 1 to Week 4 of the double-blind period as objective variables. Estimation will be performed using a restricted maximum likelihood method. An unstructured covariance structure will be used to estimate error variance. If the unstructured covariance structure fails to provide convergence, the structure that minimizes Akaike Information Criterion (AIC), among the Toeplitz, first-order autoregressive, and compound symmetry structures, will be used. The degree of freedom will be adjusted with the Kenward-Roger method.

The number of subjects, adjusted mean of the change, standard error, and two-sided 95% confidence interval in each group at each time point will be presented, and the adjusted mean and standard error will be presented in graphs. The adjusted mean between-group difference in the change at each time point for the placebo group and the MR13A9 0.5 µg/kg groups and its two-sided 95% confidence interval as well as the P value will be presented.

The assessment time points are Weeks 1 to 4.

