### 8.6.2 Rationale for the sample size

#### 8.6.2.1 Double-blind period

In a Japanese phase II clinical study (MR13A9-4), the change from baseline in the mean NRS score at Week 4 of the treatment period (mean  $\pm$  standard deviation) was  $-2.15 \pm 1.98$  in the placebo group and  $-3.22 \pm 2.09$  in the MR13A9 0.5 µg/kg group. The difference for the MR13A9 0.5 µg/kg group versus the placebo group at Week 4 of the treatment period was  $-1.04 \pm 0.35$  (adjusted mean  $\pm$  standard error).

For the primary variable of change from baseline in the mean NRS score at Week 4 of the double-blind period, its mean difference for the MR13A9 0.5 µg/kg group versus the placebo group was assumed to be  $-1.0$ , with a common standard deviation of  $2.0$ . Assuming a two-sided significance level of  $5\%$  and a statistical power of  $90\%$ , the sample size required to confirm the superiority of the MR13A9 0.5 µg/kg group to the placebo group using a two-sample t-test was calculated to be 86 subjects per group.

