#### 14.5.3.1 Primary analysis

The superiority of the MR13A9 0.5 µg/kg group to the placebo group will be confirmed by performing the analysis using a mixed-effects model for repeated measures (MMRM) with change from baseline in the mean NRS score at each time point as an objective variable; treatment group, time point, and treatment group-by-time point interaction as fixed effects; baseline mean NRS score and the presence or absence of prior treatment with nalfurafine hydrochloride as a dynamic allocation factor as covariates; and subject as a random effect.

The analysis will include all available data obtained at each time point from Week 1 to Week 4 of the double-blind period as objective variables. Estimation will be performed using a restricted maximum likelihood method. An unstructured covariance structure will be used to estimate error variance. If the unstructured covariance structure fails to provide convergence, the structure that minimizes Akaike Information Criterion (AIC), among the Toeplitz, first-order autoregressive, and compound symmetry structures, will be used. The degree of freedom will be adjusted with the Kenward-Roger method.

The adjusted mean change at each time point for each group and its two-sided 95% confidence interval will be presented. The adjusted mean difference in the change at each time point between the placebo group and the MR13A9 0.5 µg/kg group and its two-sided 95% confidence interval as well as the p value will be presented.

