- All statistical tests will be performed using a two-sided significance level of 5%; however, a two-sided significance level of 15% will be used for the analysis of between-group demographic imbalance.
- Summary statistics to be presented include the number of subjects, mean, standard deviation, minimum, median, maximum, and quartile.
- For the double-blind period, data from the start of the screening period to the end of the double-blind period will be analyzed. Over the entire study period, data from the start of the screening period to the end of the follow-up period will be analyzed.
- Unless otherwise specified, data will be summarized by group and time point for each of the double-blind and entire study periods.

5. Handling of Data

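### The primary MMRM lets the treatment effect, but not the baseline NRS slope, vary by week; a baseline-by-time point term would guard Week 4 precision at almost no cost

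*SAP*

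**What the plan says.** Protocol 14.5.3.1 and SAP 11.1.1.1 specify the same model. The fixed effects are "treatment group, time point, and treatment group-by-time point interaction as fixed effects". The covariates are "baseline mean NRS score and the presence or absence of prior treatment with nalfurafine hydrochloride as a dynamic allocation factor as covariates". Neither document lists a covariate-by-time point term or gives a reason for leaving it out.

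On the covariance the SAP says "An unstructured covariance structure will be used to estimate error variance", with REML and Kenward-Roger degrees of freedom. The modelled visits are four: "The assessment time points are Weeks 1 to 4". The confirmatory quantity is one of them: "Change from baseline in the mean NRS score at Week 4 of the double-blind period".

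The same model is reused elsewhere by cross-reference:
- both multiple-imputation analyses (SAP 11.1.1.2);
- the weekly Shiratori score, with its own baseline (SAP 11.2.1.1);
- the daily NRS and daily itch scores over Days 2 to 15 (SAP 11.1.2.4 and 11.2.1.3);
- the efficacy subgroups (SAP 11.3).

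**The concern.** Treatment may act differently each week, but the prognostic adjustment may not. If the correlation between the weekly score and baseline falls over the four weeks, the regression of change on baseline can differ between Week 1 and Week 4.

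A common slope under an unstructured covariance is not a simple average of the weekly slopes. It is a generalised least squares average that favours the week with the smallest residual variance, normally Week 1. Later weeks are correlated with Week 1 and add little. Week 4, the only confirmatory time point, is then adjusted with roughly the Week 1 slope.

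Two things are at stake. One is precision from a baseline the trial already collects. The other is part of the missing-at-random correction for subjects who leave before Week 4. The two imputation analyses refit the same model, so neither tests this restriction in the analysis model.

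**Working it through.** **The plan's own figure.** Protocol 8.6.2.1 assumes a difference of −1.0, SD 2.0, two-sided 5% and 90% power, and arrives at 86 per group. The noncentral t gives power 0.8999 at 85 and 0.9032 at 86, so 86 reproduces.

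**Inputs not in the documents.** Baseline SD, weekly SDs, correlations with baseline and residual correlations are not given. Everything below that uses them is an assumption.

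**Formulas.**
- Weekly slope of change on baseline: β_t = r_t·SD_t/SD_B − 1, where r_t is the correlation of the Week t score with baseline.
- Residual variance: SD_t²(1 − r_t²).
- Common slope: b = (1′S⁻¹β)/(1′S⁻¹1), where S is the residual covariance.
- Excess Week 4 variance: (β₄ − b)²·SD_B² / residual variance at Week 4.

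**Case with drift.** SD_B = 1.4; score SD rising from 1.7 to 2.2; r falling from 0.8 to 0.45. Weeks 2 and 3 are interpolated: SD 1.87 and 2.03, r 0.68 and 0.57.
- β₁ = 0.8 × 1.7/1.4 − 1 = −0.029. β₄ = 0.45 × 2.2/1.4 − 1 = −0.293.
- Week 4 residual variance = 4.84 × (1 − 0.2025) = 3.860.

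| Residual correlation | Week 1 weight | b | Excess Week 4 variance |
|---|---|---|---|
| AR(1), 0.7 | 0.91 | −0.055 | 0.238² × 1.96/3.860 = 2.9% |
| AR(1), 0.85 | 1.27 | −0.008 | 0.285² × 1.96/3.860 = 4.1% |
| Exchangeable, 0.7 | 1.06 | +0.022 | 5.0% |
| Exchangeable, 0.85 | 1.43 | +0.097 | 7.7% |

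Other baseline SDs and paths through Weeks 2 and 3 move these figures somewhat. About 3–5% is a fair summary, with about 8% as the exchangeable extreme.

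**Case with nearly equal slopes.** With r falling only from 0.65 to 0.5, the excess is roughly 0 to 0.3%.

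**Power at 86 per arm.** Take SD 2.0 as the common-slope residual SD. Removing a 5% excess gives SD 2.0/√1.05 = 1.952 and power 91.6%, against 90.3%: 1.3 points, or about 86 × 0.05 ≈ 4 subjects per arm. An excess of 0.1% is worth 0.03 points. The 8% extreme gives 92.3%, or 2.0 points.

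**Wider assumed grid.** Total SD of change was set to 1.3, 1.6, 1.85 and 2.0 at Weeks 1 to 4, baseline SD to 1.0–2.0, and AR(1) correlation to 0.6 or 0.85. The ratio of Week 4 SEs, common over week-specific slopes, is:
- equal slopes: 1.000;
- mild drift (−0.25 to −0.40): 1.002–1.013;
- moderate drift (−0.10 to −0.40): 1.006–1.046;
- strong drift (0 to −0.60): 1.025–1.153.

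At baseline SD 1.5 and correlation 0.85, power (common against week-specific) is 91.5% against 92.8% under moderate drift, and 91.6% against 95.5% under strong drift.

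**Simulation.** 172 subjects, REML, unstructured covariance, baseline SD 1.5, 1,500–2,500 runs per scenario, and a t reference with 165 df in place of Kenward-Roger. The comparison model has week-specific covariate effects.
- Complete data: absolute bias at most 0.012 for both models (Monte Carlo SE about 0.008). Type I error of the planned model is 0.0496 with equal slopes and 0.0496 with strong drift.
- Equal slopes: the interaction model's mean SE is about 0.4% larger, and it has the smaller SE in only 17–20% of runs.
- About 11% missing-at-random dropout, linked to baseline in opposite directions by arm: the planned model is biased toward no effect by 0.035 (moderate drift) and 0.073 (strong drift), against 0.005 or less. Power is 87.5% against 91.1%, and 83.6% against 93.5%.

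**Phase II check.** Protocol 8.6.2.1 gives Week 4 SDs of 1.98 and 2.09 and an adjusted SE of 0.35. Protocol 1.3.2.2 and 1.4.1 give group sizes of 61 active and 247 − 184 = 63 placebo. Unadjusted SE = √(1.98²/63 + 2.09²/61) = 0.366. The variance ratio is (0.35/0.366)² ≈ 0.915, or 0.89–0.94 allowing for rounding, so all adjustment together removed about 6–11%. The phase II model form is not given, so this is only indicative.

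**The case against.** A reader might infer that the planned Week 4 estimate is wrongly adjusted. The documents do not support that: subjects are randomised, and with complete data the planned contrast is unbiased with correct type I error.

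A reader might also infer that the interaction always gains precision and costs nothing. It does not. With equal slopes it loses about 0.4% in SE, and nothing in the documents shows which case applies. Protocol 8.2.5 says the phase II effect was constant after Week 4, which suggests response was still developing before then, but it gives no slopes.

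The 3–5% figure sits at a corner. A Week 1 slope of −0.029 means almost no regression to the mean in the first week, although inclusion criterion 6 selects on a mean NRS above 4.0 in the same seven days that define baseline. In that case the planned adjustment removes only about 0–1.5% of Week 4 variance, against the indicative 6–11% in phase II. More regression to the mean at Week 1 would narrow the drift. The larger losses in the wider grid need slopes running from 0 to −0.60 or a baseline SD up to 2.0.

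The dropout bias needs slope drift together with dropout that depends on baseline in opposite directions by arm. Nothing in the documents points to that pattern. No size has been worked out for the prior-nalfurafine-by-week term on its own.

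All of this stands, and it limits the point to a refinement. It does not remove the restriction, for which the plan gives no reason, or the favourable balance between a very small cost and a possible gain.

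**Conclusion.** The restriction is real and its mechanism checks out: Week 1 carries about 0.6 to 1.5 of the weight in the common slope across the assumed inputs, so Week 4 is adjusted with roughly the Week 1 slope. This does not invalidate the primary test or the sample size.

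The likely consequence is lost precision, from nil with equal slopes to about 3–5% of Week 4 residual variance when the correlation with baseline falls from 0.8 to 0.45. Within that range it is worth at most about 1.3 power points at 86 per arm. A modest bias toward no effect is possible only if slope drift and arm-specific, baseline-dependent dropout occur together. Every size rests on assumed SDs and correlations. This is a desirable refinement, not an error.

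**What to change.** Before unblinding, add a baseline mean NRS-by-time point interaction to the Weeks 1–4 primary MMRM, in matching words in protocol 14.5.3.1 and SAP 11.1.1.1. Carry it to the two multiple-imputation analyses in SAP 11.1.1.2 and, as the score's own baseline-by-time point, to the weekly Shiratori MMRM in SAP 11.2.1.1. Prior nalfurafine-by-time point is optional.

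State that the term does not pass automatically to the Days 2–15 models in SAP 11.1.2.4 and 11.2.1.3. With 14 days it would add 13 parameters per covariate there, beside a 14 × 14 unstructured matrix. Say also whether it applies in the SAP 11.3 subgroups, which reuse the primary model.

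The change alters a pre-specified confirmatory model. SAP version 3.0 is dated October 24, 2022, and the documents do not say when the double-blind data were unblinded. If that has already happened, keep the planned model as primary and report the interaction model as a supplementary analysis.

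The cost is one clause in each document, three extra parameters with 172 subjects, and an SE increase of about 0.4% or less if the slopes turn out equal.

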#### **8.5.3.5 Randomization of subjects**

Based on the treatment assignment table prepared by the person responsible for treatment assignment, the subject registration center will randomly assign subjects eligible for tertiary registration to either the MR13A9 0.5 µg/kg or placebo group at a ratio of 1:1 by a dynamic allocation method using two stratification factors: Prior treatment with nalfurafine hydrochloride notified by the medical institution (for ≥ 2 consecutive weeks in the year prior

---

to the informed consent procedure) and specific signs or symptoms occurring during the screening period ([Appendix 4](#)) confirmed before dialysis on the start day of treatment.

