#### **14.5.4 Secondary endpoints**

1) Itch score based on the Shiratori's severity criteria

The mean itch score and change from baseline at each time point will be calculated using the same calculation formula as that for the mean NRS score and change from baseline shown in “[14.5.1 Primary endpoint](#).”

For changes from baseline, the same analysis as “[14.5.3.1 Primary analysis](#)” will be performed on the data obtained up to Week 4 of the double-blind period. However, the covariate of the model will be the baseline of the data to be analyzed. The same analysis as “[14.5.3.3 1\) Change from baseline in the mean NRS score](#)” will be performed.

For measurements, the same analysis as “[14.5.3.3 2\) Mean NRS score](#)” will be performed.

2) Overall Skindex-16 score and total 5-D itch scale score

For changes from baseline, analysis of covariance with treatment group as a fixed effect and baseline score as a covariate will be performed on the data obtained at the end of the double-blind period. The same analysis as “[14.5.3.3 1\) Change from baseline in the mean NRS score](#)” will be performed.

For measurements, the same analysis as “[14.5.3.3 2\) Mean NRS score](#)” will be performed.

3) PGIC(Patient Global Impression of Change)

The number and percentage of subjects with global symptoms will be presented. For the double-blind period, a two-sample Wilcoxon test will be used for comparisons between the placebo group and the MR13A9 0.5 µg/kg group.

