5.7.2 Handling of data in tabulation at the final assessment point

- In the double-blind period, efficacy data (Skindex-16, 5-D itch scale, and PGIC) obtained at Weeks 1 to 4 (or at the time of withdrawal during the double-blind period before Week 4) and safety data obtained at Weeks 1 to 6 (or at the time of withdrawal during the double-blind period) will be included in the tabulation. Data for observations and tests performed at the latest time point within 10 days after the day of the final dose during the double-blind period will be used as the data at the end of the double-blind period. Data for observations and tests performed at unscheduled visits will be excluded from the tabulation.
- For the entire study period, data from Weeks 1 to 58 (or at the time of withdrawal during the extension period) will be included in the tabulation. Data for observations and tests performed at the latest time point within 10 days after the day of the final dose during the extension period will be used as the data at the end of the extension period. Data for observations and tests performed at unscheduled visits will be excluded from the tabulation.

6. Statistical/Analytical Issues**6.1 Adjustments for Covariates**

The change from baseline in the mean NRS score at Week 4 of the double-blind period, the primary variable, will be analyzed using the baseline mean NRS score and the presence of prior treatment with nalfurafine hydrochloride, a dynamic allocation factor, as a covariate. For details, refer to "[11.1.1 Primary variable](#)." If an imbalance is observed in the subject demographics of the FAS, the primary analysis set for efficacy, a supplementary analysis will be performed with

additional items showing the imbalance as the covariates in the primary analysis.

For the changes from baseline in the itch score based on the Shiratori's severity criteria, changes from baseline in Skindex-16, and changes from baseline in 5-D Itch Scale, an analysis will be performed using the baseline as a covariate for each item. Details are shown in "[11.2.1.1 Change from baseline in the mean itch score](#)," "[11.2.2.1 Changes from baseline in Skindex-16](#)," and "[11.2.3.1 Changes from baseline in 5-D itch scale](#)," respectively.

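### Subjects are allocated on two factors, but the primary MMRM adjusts for one and the Skindex-16 and 5-D ANCOVAs for neither, so the tests are slightly conservative if an omitted factor is prognostic

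*SAP*

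**What the plan says.** **Allocation.** Protocol 8.5.3.5 assigns subjects 1:1 "by a dynamic allocation method using two stratification factors". The first is prior nalfurafine use. The second is "specific signs or symptoms occurring during the screening period", confirmed before dialysis on the first treatment day.

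**Primary model.** Protocol 14.5.3.1 has treatment, time point and their interaction, with baseline mean NRS and "presence or absence of prior treatment with nalfurafine hydrochloride as a dynamic allocation factor as covariates". SAP 11.1.1.1 gives the same terms ("presence or absence of prior treatment with nalfurafine hydrochloride as a dynamic allocation factor as a covariate"), and SAP 6.1 says the primary variable is analysed "using the baseline mean NRS score and the presence of prior treatment with nalfurafine hydrochloride, a dynamic allocation factor, as a covariate". The signs/symptoms factor is in none of the three.

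**Skindex-16 and 5-D.** Protocol 14.5.4 specifies "analysis of covariance with treatment group as a fixed effect and baseline score as a covariate". SAP 11.2.2.1 repeats this for Skindex-16, and SAP 11.2.3.1 applies it to the 5-D. Neither allocation factor appears.

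**Shiratori score.** Protocol 14.5.4 and SAP 11.2.1.1 call for the primary analysis again, but with the item's own baseline as the covariate. SAP 6.1 says only that "an analysis will be performed using the baseline as a covariate for each item". It is unclear whether nalfurafine stays in this model.

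**Subgroups.** Within the nalfurafine subgroups, SAP 11.3 keeps baseline NRS alone.

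**Supplementary rule.** SAP 6.1 adds covariates in a supplementary analysis: "If an imbalance is observed in the subject demographics of the FAS". SAP 9.1 tabulates signs/symptoms but tests imbalance only for prior nalfurafine, dry weight category and mean NRS. Apart from that, the SAP uses the factor only as a safety subgroup (12.5).

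**The concern.** The primary model includes nalfurafine expressly because it is an allocation factor. The second factor has the same status under Protocol 8.5.3.5 but is dropped, and neither document says why.

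Dynamic allocation forces the arms to be alike on the factor, so the treatment difference varies less from trial to trial than it would under simple randomisation. A model without the factor cannot see this. It leaves the factor's variance in the residual and reports a standard error that is too large, to the extent that the factor predicts the outcome. The interval is then too wide and the test rejects too rarely under the null.

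The supplementary rule in SAP 6.1 does not help. It is triggered by imbalance, whereas the conservatism comes from balance, and this factor is not among the variables tested.

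At stake are some precision, and agreement between the way the trial is randomised and the way it is analysed. The validity of a positive result is not in question.

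**Working it through.** **Inputs from the documents.** Protocol 8.6.2.1: difference 1.0, SD 2.0, two-sided 5%, 90% power, two-sample t-test, 86 per group. Protocol 8.6.1: 172 in total.

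**Assumption.** R² is the share of outcome variance explained by the omitted factor. The documents give neither this nor the factor's prevalence, so a range is used. For a binary factor with prevalence p and effect b on the NRS change, R² = b²p(1−p)/SD². At p = 40%:
- b = 0.5 gives 0.25 × 0.24 / 4 = 1.5%.
- b = 1.0 gives 1 × 0.24 / 4 = 6%.

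**Step 1: reproduce the sample size.** The noncentral t gives power 89.99% at 85 per group and 90.32% at 86, so the plan's 86 is confirmed.

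**Step 2: effect of omitting one balanced factor.**
- Reported SE = 2.0 × √(2/86) = 0.305.
- True SE = 0.305 × √(1 − R²).
- Type I error = 2 × P(t₁₆₈ > 1.974/√(1 − R²)).
- Power comes from the noncentral t at a difference of 1.0, with critical value 1.974/√(1 − R²) when the factor is omitted and 1.974 when it is included.

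| Assumed R² | True SE | Reported SE too large by | Type I error, omitted | Power, omitted | Power, included |
|---|---|---|---|---|---|
| 0 | 0.305 | 0 | 5.0% | 90.3% | 90.3% |
| 1.5% | 0.303 | 0.8% | 4.8% | 90.5% | 90.7% |
| 6% | 0.296 | 3.1% | 4.3% | 91.0% | 92.0% |
| 10% | 0.289 | 5.4% | 3.9% | 91.5% | 93.0% |

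Power with the factor omitted never falls below the planned 90.3%, because the sample size already rested on an unadjusted test.

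**Step 3: check by simulation.** This used 10,000 trials per scenario, 172 subjects, minimisation with a 0.9 biased coin, nalfurafine prevalence 50% with effect 0.5, and one Week 4 outcome. With a signs/symptoms effect of 1.0:

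| Prevalence | SE, both factors | SE, nalfurafine only | Type I, both | Type I, nalfurafine only | Power, both | Power, nalfurafine only |
|---|---|---|---|---|---|---|
| 40% | 0.293 | 0.302 | 4.9% | 4.3% | 92.1% | 91.0% |
| 20% | 0.296 | 0.302 | 5.2% | 4.7% | 91.9% | 91.0% |

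Monte Carlo error on type I error is about 0.2 points. With no signs/symptoms effect the two models agree.

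**Step 4: omitting both factors, as the ANCOVAs do.** A separate simulation assumed prevalences of 40% and 30%, a 0.8 biased coin, and the same R² for each factor (20,000 trials per scenario):

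| R² per factor | Type I, neither in model | Type I, nalfurafine only | Type I, both in model |
|---|---|---|---|
| 0 | 4.9% | 5.0% | 5.0% |
| 2% | 4.6% | 4.8% | 5.1% |
| 5% | 3.7% | 4.2% | 4.8% |
| 10% | 2.8% | 3.8% | 5.0% |

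No baseline score was modelled here. The ANCOVAs adjust for it, which would absorb part of the effect.

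**Step 5: could the imbalance rule bring the factor in?** In the Step 3 simulation, the arms differed in the number of subjects with signs/symptoms by 0.7 on average and by at most 2 in 95% of trials. The difference never exceeded 6 in 50,000 trials. Even a difference of 6, such as 20/86 against 14/86, gives Fisher p = 0.34, above the 15% level the SAP uses for imbalance. The rule would almost never select this factor even if it were tested.

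**The case against.** The strongest reply is that the factor was chosen for safety. Appendix 4 of the protocol lists events such as dizziness, syncope, falls and somnolence. The same list defines the adverse events of special interest and a safety subgroup, but no efficacy subgroup. Balancing it for safety comparability while adjusting the itch model for itch-related covariates is coherent, and nothing in the documents shows that it predicts change in NRS. This stands as a possible rationale, but the plan does not state it. It also does not alter the fact that the standard error should reflect how subjects were allocated.

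The larger figures also need strong assumptions. R² of 6% at 40% prevalence means a 1.0-point shift, equal to the whole assumed drug effect, and 10% means √(0.10 × 4/0.24) = 1.29 points. This is fair: the milder rows of the table are the more credible ones.

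Finally, the primary model is prespecified consistently in three places, and SAP 6.5.2 treats every other endpoint as a reference. Both are true. They limit the weight of the point without answering it. The Shiratori wording is a separate drafting matter and adds no weight here.

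**Conclusion.** The point holds. Allocation uses two factors, the primary MMRM carries one, and the Skindex-16 and 5-D ANCOVAs carry neither. No reason is given, and the supplementary rule will not correct it.

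The consequence is small and always in the conservative direction. For the primary test, type I error lies between 5.0% and 3.9% for an assumed R² of 0 to 10%, and the power forgone lies between 0 and 1.5 points (93.0% − 91.5%). There is no inflation of type I error, no bias and no threat to the planned power. The ANCOVAs can be more conservative, but no confirmatory decision depends on them.

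The mismatch is plain from the text. Its size rests on assumed prognostic strength, prevalence and biased-coin probability, and on a single-time-point model standing in for the MMRM. The change should be made because it costs almost nothing and makes the analysis follow the design.

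**What to change.** - **Primary MMRM** (Protocol 14.5.3.1; SAP 6.1 and 11.1.1.1): add signs/symptoms during screening (no/yes) as a covariate. The multiple-imputation and daily NRS analyses then follow by reference.
- **Nalfurafine subgroups** (SAP 11.3): keep the signs/symptoms term alongside baseline NRS.
- **Skindex-16, 5-D and Shiratori models** (Protocol 14.5.4; SAP 6.1, 11.2.1.1, 11.2.1.3, 11.2.2.1 and 11.2.3.1): add both allocation factors.
- **Shiratori wording:** state whether the item's own baseline replaces only the NRS baseline.
- **If the double-blind data are already unblinded:** leave the primary model as it is, and report the two-factor model as a labelled sensitivity analysis. The documents do not say when unblinding took place.

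The cost in the primary model is one term and one degree of freedom. The factor is already collected for allocation, and the sample size does not change. Because the model text in the protocol is affected, the change needs a protocol amendment or an entry in SAP section 15.

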11.1.2.4 Change from baseline in the daily NRS score

The same analysis as described in “[11.1.1.1 Primary analysis](#)” will be performed using the data obtained from Days 2 to 15 of the double-blind period. The analysis will include all available data obtained at each time point from Days 2 to 15 of the double-blind period as objective variables.

The assessment time points are as follows:

- Double-blind period: Days 2 to 15

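### The primary MMRM as written is over-parameterised, and its fallback allows only common-variance structures, so the Week 4 standard error could be wrong in either direction if the fallback is used

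*SAP*

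**What the plan says.** SAP 11.1.1.1, matching protocol 14.5.3.1, fits change from baseline in weekly mean NRS to "all available data obtained at each time point from Week 1 to Week 4 of the double-blind period". The fixed effects are treatment, time point and their interaction. The covariates are baseline mean NRS and prior nalfurafine treatment. The model description ends with "and subject as a random effect".

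The next paragraph adds: "An unstructured covariance structure will be used to estimate error variance". The fallback is conditional: "If the unstructured covariance structure fails to provide convergence", the lowest-AIC structure "among the Toeplitz, first-order autoregressive, and compound symmetry structures, will be used". Inference is model-based: "The degree of freedom will be adjusted with the Kenward-Roger method". No heterogeneous-variance version and no robust standard error is named.

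The same model is reused in both multiple-imputation sensitivity analyses (SAP 11.1.1.2), in the subgroups (SAP 11.3) and in the daily analysis (SAP 11.1.2.4), which takes "all available data obtained at each time point from Days 2 to 15".

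**The concern.** There are two linked problems.

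First, an unstructured matrix already contains every variance and covariance among the four visits. A random subject intercept adds a constant to all of them, which the unstructured matrix can absorb. The intercept variance therefore cannot be separated from the rest. A programmer who codes both terms asks the software to estimate a redundant parameter, a recognised cause of non-convergence.

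Second, non-convergence is what activates the fallback. In standard form, Toeplitz, AR(1) and compound symmetry each have a single variance for all visits, so AIC can only choose among structures that share this restriction. The Week 4 standard error then comes from a variance pooled over Weeks 1 to 4. If Week 4 differs from that average, the standard error, confidence interval and p value are wrong at the one time point that decides the trial. The Kenward-Roger adjustment does not repair a misspecified covariance structure.

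**Working it through.** **Inputs from the documents.** Week 4 SD 2.0, difference −1.0, 86 per group, 90% power (protocol 8.6.2.1); two-sided 5% level (SAP section 4); four weekly visits (SAP 11.1.1.1). **Not in the documents:** SDs of change at Weeks 1, 2 and 3. These are assumed below.

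**The plan's own figure.** For a two-sample t-test with these inputs, noncentral-t power is 0.8999 at 85 per group and 0.9032 at 86. The stated 86 is reproduced and is not affected by this point.

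**Identifiability.** Count the parameters and take the rank of the map from parameters to the distinct elements of the 4×4 marginal covariance.

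| Structure | Alone: parameters / rank | With random intercept: parameters / rank |
|---|---|---|
| Unstructured | 10 / 10 | 11 / 10 |
| Toeplitz | 4 / 4 | 5 / 4 |
| AR(1) | 2 / 2 | 3 / 3 |
| Compound symmetry | 2 / 2 | 3 / 2 |

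Only AR(1) is identifiable beside a random intercept, and even then all four weeks share one variance. Under unstructured errors the total covariance remains identified, so a fit that converges gives the same Week 4 difference and standard error with or without the redundant term.

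**Effect of the fallback.** With complete balanced data and ignoring covariates, the Week 4 contrast is the difference in Week 4 means, whichever structure is used. Its standard error is sqrt(2 × Week 4 variance / 86). With the Week 4 variance left free, this is 2.0 × sqrt(2/86) = 0.305. Under a common variance, approximately:

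- SE ratio = sqrt(mean of the four weekly variances) / Week 4 SD
- Type I error = 2 × (1 − Φ(1.96 × ratio))

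Example for SDs 1.2, 1.5, 1.8, 2.0: mean variance = (1.44 + 2.25 + 3.24 + 4.00)/4 = 2.7325; square root 1.653; ratio 1.653/2.0 = 0.827; 1.96 × 0.827 = 1.62; type I error 10.5%.

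| Assumed SDs, Weeks 1–4 | SE ratio | Type I error |
|---|---|---|
| 1.8, 1.9, 1.95, 2.0 | 0.957 | 6.1% |
| 1.6, 1.8, 1.9, 1.95 | 0.932 | 6.8% |
| 1.5, 1.7, 1.9, 2.0 | 0.893 | 8.0% |
| 1.2, 1.5, 1.8, 2.0 | 0.827 | 10.5% |
| 2.0, 2.0, 2.0, 2.0 | 1.000 | 5.0% |
| 2.3, 2.2, 2.1, 2.0 | 1.08 | 3.5% |

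**Check on the averaging.** Instead of averaging, the closest Toeplitz, AR(1) and compound-symmetry matrices (Kullback-Leibler) were fitted to assumed true covariances with AR(1) correlation 0.7 or 0.85. For SDs 1.6, 1.8, 1.9, 2.0 the Week 4 standard error is 0.277 to 0.279, with type I error about 7.3% to 7.5%. For a steeper rise (1.0, 1.4, 1.8, 2.0) it is 0.242 to 0.244, about 12%. For the falling pattern it is 0.328 to 0.329, about 3.5%. In the rising patterns averaging matches compound symmetry and is slightly optimistic for the other two.

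**Daily model.** An unstructured matrix over 14 days has 14 × 15/2 = 105 parameters, so the fallback is more likely to be needed there, especially in subgroups.

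**The case against.** The strongest reply has four parts.

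- *The random-effect phrase is loose wording.* The SAP gives one covariance structure, says it is for error variance, and specifies no random-effects covariance. An ordinary MMRM with subject as the clustering unit is the natural reading. That is fair, and it makes this half a clarification. But the text for a confirmatory test should not depend on the programmer choosing the non-literal reading.
- *The fallback is unlikely to be used.* With 172 subjects, four visits and 10 covariance parameters, an unstructured fit should normally converge. This stands for the model without the random intercept. It is less reassuring for the model as literally written, and the probability of failure is not known for either.
- *The direction is unknown.* A reader might infer that the fallback would necessarily understate the Week 4 standard error. The documents do not support that: they give SDs of change at Week 4 but none for Weeks 1 to 3. Rising variance is plausible, because Week 1 adjoins the baseline window and Week 4 is three weeks further away, but it remains an assumption. The remark in protocol 8.2.5 that the phase II effect was constant after Week 4 concerns the size of the effect and does not settle the variances.
- *A cross-check exists.* SAP 11.1.2.1 includes a two-sample t-test of change at Week 4 using that week's own variance. A badly wrong MMRM standard error would show beside it. But it is a reference analysis and does not replace the confirmatory test.

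The daily model is also only a reference analysis (SAP 6.5.2), so its convergence cannot affect the primary conclusion.

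**Conclusion.** The point holds in conditional form. On a literal reading the primary model is over-parameterised by one parameter. A reader might infer that the primary analysis cannot be estimated or is invalid; that does not follow, because a fit that converges gives the intended Week 4 estimate and standard error.

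The substantive weakness is the fallback. If it is used and the variance of change differs across Weeks 1 to 4, the Week 4 standard error is wrong. Over the tabulated patterns it runs from about 17% too small (type I error 10.5%) to about 8% too large (3.5%), and it is correct if variance is flat. The steeper assumed rise takes type I error to about 12%. These figures assume complete data and no covariate adjustment, and the Week 1 to 3 SDs are not from the documents. If the unstructured fit converges, nothing changes. The amendment is worth making because a stated rule for the deciding test carries an avoidable error; it is not a reason to doubt the design or the sample size.

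**What to change.** In both SAP 11.1.1.1 and protocol 14.5.3.1:

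1. Replace the random-effect phrase with a statement that within-subject errors over Weeks 1 to 4 follow an unstructured covariance matrix, with subject as the blocking unit and no separate random intercept.
2. Replace the fallback list with heterogeneous Toeplitz, heterogeneous AR(1) and heterogeneous compound symmetry, chosen by AIC, keeping Kenward-Roger degrees of freedom. Each leaves the Week 4 variance free.

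The same wording should carry over to the daily model in SAP 11.1.2.4. If the double-blind analysis has already been run, the report should say which covariance structure was used.

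The cost is a few sentences in two documents. The fallback fits gain three variance parameters with four visits (four variances instead of one) and 13 in the 14-day model (14 instead of one). Data collection and sample size are unaffected.
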